4.2. Selection of Subject Population

Eligible subjects must provide written consent to participate in this clinical trial of their own free will after being fully informed of the contents of the trial based on the written information and informed consent form.

After obtaining written informed consent from each subject, the investigator or subinvestigator will screen the subject within 21 days before the first investigational drug infusion. The investigator will assess subject eligibility based on the inclusion criteria and the exclusion criteria below.

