5.3.7 Recording of Adverse Events

All AEs and SAEs occurring after the subject has signed the ICF through the End of Study must be fully recorded in the subject's CRF and SAE form if applicable. If no AE has occurred during the study period, this should also be indicated in the CRF.

It is responsibility of the Investigator to ensure that AEs are appropriately recorded.

At each visit, AEs will be elicited by asking the individual a non-leading question such as "Do you feel different in any way since the last visit?". Moreover, AEs will also be collected through directly observed events or spontaneously volunteered by the subject. Clearly related signs, symptoms and abnormal diagnostic procedures should preferably be grouped together and recorded as a single diagnosis or syndrome wherever possible.

The following variables must be recorded on the AE CRF entry:

1. The verbatim term (a diagnosis is preferred)
2. Date/time of onset
3. Date/time of resolution
4. Severity (mild, moderate, severe)
5. Causality (unrelated, doubtful/unlikely, possible, probable, definite)*
6. Seriousness (yes, no)
7. Action taken (with regard to investigational product)
8. Other action (to treat the event)
9. Outcome and sequel (follow-up on AE)

**Causality assessment will be only made when the AE occurs after the subject has initiated at least one infusion of the investigational product. Any AE occurring before subject's exposure to investigational product will be always labeled as "unrelated".*

In addition to the Investigator's own description of the AEs, each AE will be encoded by the Sponsor (or Contract Research Organization [CRO]) according to the Medical Dictionary for Regulatory Activities (MedDRA®).

For example, a laboratory test abnormality considered clinically relevant, e.g., causing the subject to withdraw from the study, requiring treatment or causing apparent clinical manifestations, or judged relevant by the Investigator, should be reported as an AE. Each

event must be described in detail along with start and stop dates, severity, relationship to investigational product, action taken and outcome. Each event must be adequately supported by documentation as it appears in the subject's medical or case file.

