11.1 Adverse Events

Definition of Adverse Events

Adverse Event:
	
An AE is any untoward medical occurrence in a subject or clinical investigation subject administered a pharmaceutical product, which does not necessarily have a causal relationship with this treatment.
 
An AE can therefore be any unfavorable and unintended sign (including an abnormal laboratory finding), symptom, or disease temporally associated with the use of a medicinal product, whether or not considered related to the IMP.
 
In this protocol, non-serious COPD exacerbation will not be considered as adverse events unless SAE.

TEAE for GTI 1401
	
Treatment emergent adverse events (TEAE) for GTI 1401 will defined as any adverse event occurred after or on the first study drug infusion of GTI 1401 to the final visit of GTI 1401.
 
For any subject, all AEs that occur at any time from the beginning of Alpha-1 MP administration until the final visit of the clinical trial will be considered as TEAE.
 
All tables regarding to Adverse Events are restricted to TEAE.

TEAE for GTI1401-OLE
	
Treatment emergent adverse events (TEAE) for GTI 1401-OLE will defined as any adverse event occurred after or on the first study drug infusion of GTI 1401-OLE to the final visit of GTI 1401-OLE or adverse event which continue from GTI 1401 to GTI 1401-OLE.
 
For any subject, all AEs that occur at any time from the beginning of Alpha-1 MP administration until the final visit of the clinical trial will be considered as TEAEs
 
All tables regarding to Adverse Events are restricted to TEAE.

Adverse Drug Reaction (ADR):
	
The phrase “responses to a medicinal product” means that a causal relationship between a medicinal product or study treatment and an AE is at least a reasonable possibility, that is, the relationship cannot be ruled out.

	
When an AE is classified, assessing causal relationship by the Investigator, as “definitive”, “probable”, “possible” or “doubtful/unlikely”, the event will be defined as a suspected ADR. When the causal relationship is labeled “Unrelated”, then it will be considered that the AE is not imputable to the study treatment and it is not a suspected ADR.

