
Serious Adverse Events (SAEs):
	
Any event reported on the AE CRF form with the serious field ticked “Yes”.
 
A SAE is any untoward medical occurrence that at any dose:
 
Results in death
 
Is life-threatening
 
Note: The term “life-threatening” in this definition refers to an event in which the subject is at risk of death at the time of the event; it does not refer to an event that hypothetically might cause death if it were more severe.
 
Requires inpatient hospitalization or prolongation of existing hospitalization
 
Results in persistent or significant disability/incapacity
 
Is a congenital anomaly/birth defect

Events of Special Interest :
	
Events of special interest include the following:
 
All COPD exacerbations occurring during the study will be recorded. Each subject will be assessed for signs and symptoms of exacerbations at each study visit as specified in Appendix 1 and Appendix 2. Given that COPD exacerbations are part of the natural history of AATD, COPD exacerbations will not be reported as AEs unless a COPD exacerbation meets the criteria of a SAE. If an exacerbation meets criteria for a SAE, it will be reported as such, and the standard of care should be followed. Results from standard of care should be obtained and reported.

Adverse events with incomplete start dates will be considered treatment emergent (TEAE) if:

- Day and Month are missing and the year is equal to or after the year of the first study drug dose date of each study (1401/1401-OLE);

- Day is missing, month is present and the month is equal or after the month of first dose of each study (1401/1401-OLE) and the year is equal or after the year of first dose date of each study (1401/1401-OLE);
- Day is missing and the year is equal to the year of the first infusion date of each study (1401/1401-OLE) and the month is equal to or after the month of the first infusion date of each study (1401/1401-OLE);
- Complete date is missing.

The AE tables will include the number and percentage of subjects by MedDRA primary System Organ Classes (SOC) - sorted by alphabetical order, MedDRA Preferred Terms (PT) - sorted by alphabetical order. A subject with more than one occurrence of the same adverse event in a particular system organ class/preferred term will be counted only once in the total of those experiencing adverse events in that particular system organ class/preferred term.

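### The rule for adverse events with incomplete start dates ignores the recorded end date, so an event known to have ended before the first infusion can be tabulated as treatment-emergent

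*SAP*

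**What the plan says.** SAP 11.1 gives four conditions under which an AE with an incomplete start date is treated as emergent.

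- Day and month missing: "the year is equal to or after the year of the first study drug dose date of each study (1401/1401-OLE").
- Day missing (two overlapping bullets): the month and year are compared with those of the first dose. The second bullet requires the same year and that "the month is equal to or after the month of the first infusion date of each study (1401/1401-OLE").
- Whole date missing: "Complete date is missing" is sufficient by itself.

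None of these refers to the end of the event. SAP 5.2 (Handling of Missing values) adds no end-date rule.

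The definition that these conditions serve is in the same section. A GTI1401 TEAE is "any adverse event occurred after or on the first study drug infusion of GTI 1401 to the final visit of GTI 1401". For the extension, the definition covers events on or after the first extension infusion and also any "adverse event which continue from GTI 1401 to GTI 1401-OLE". All AE tables are restricted to TEAEs.

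On collection, Protocol 5.3.7 states: "All AEs and SAEs occurring after the subject has signed the ICF through the End of Study must be fully recorded". Protocol 4.2 has the investigator "screen the subject within 21 days before the first investigational drug infusion". "Date/time of resolution" is one of the variables that Protocol 5.3.7 requires on the AE form, and the AE listing in the SAP's Layout Plan (11.1.7) prints it.

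**The concern.** Treating an event as emergent when its timing is unknown is a normal conservative default. Here the default also applies when the timing is known well enough to settle the matter: an end date before the first infusion proves that the event was not treatment-emergent, and the rule discards that proof. The database will hold pre-dose events, because collection starts at consent.

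Safety is the primary objective, the AE tables contain only TEAEs, and the target is at least 3 subjects. A rule that decides entry to those tables should not admit events that the SAP's own definition excludes.

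**Working it through.** The plan gives no figure for this point, so there is none to reproduce. The check applies the conditions literally to dates.

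**Worked dates.** Assume a first GTI1401 infusion on 20 September 2016. The earliest screening day is then 30 August (20 September minus 21 days).

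| Recorded start | Recorded end | Condition met | Rule | Definition |
|---|---|---|---|---|
| September 2016, day unknown | 10 September 2016 | month 9 ≥ 9, same year | TEAE | not a TEAE: ended 10 days before infusion |
| 2016, day and month unknown | 10 September 2016 | 2016 ≥ 2016 | TEAE | not a TEAE |
| wholly missing | 10 September 2016 | date missing | TEAE | not a TEAE |

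**How often the rule misfires, given an incomplete start date.** Assumptions: every first-infusion date from 22 January 2016 to 31 January 2017 is equally likely (376 dates, inside the planned trial period), and a screening AE starts on any of the 21 days before infusion with equal chance and ends before infusion. That gives 376 × 21 = 7,896 cases.

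- Day missing: 5,124 / 7,896 = 64.9% become GTI1401 TEAEs. As a rough check, the mean lag is (1 + 21) / 2 = 11 days, and 1 − 11 / 30.4 ≈ 64%.
- Day and month missing: 7,665 / 7,896 = 97.1%. The 231 exceptions are the first infusions on 1 to 21 January 2017 paired with a December onset: 21 + 20 + … + 1 = 231.
- Whole date missing: 7,896 / 7,896 = 100%.

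These are conditional percentages. They do not say how many AEs will have incomplete start dates, and the documents give no figure for that.

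**Effect on the tables.** Each misclassified event adds one to the number of AEs. The number of subjects with at least one AE changes only if the subject has no other TEAE. In that case the shift is 1/3 = 33.3 points with 3 subjects, or 1/4 = 25.0 points with 4 (4 is an assumed size; the plan states a minimum of 3).

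**Drug reactions.** Protocol 5.3.7 labels any AE before first exposure as unrelated, so it stays out of the ADR tables. The exception is a missing relationship, which SAP 5.2 and 11.1 count as related.

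**Extension, conditional.** Suppose that GTI1401 AE records are also run through the extension derivation. Take the first extension infusion as day 56, here 15 November 2016. An AE dated November 2016 that ended on 8 November meets the conditions for both studies, although it neither began after extension dosing nor continued into it. Over 376 × 56 = 21,056 cases of AEs that began and resolved between the two first infusions, both rules are met in 4,850 (23.0%) with the day missing, 19,460 (92.4%) with day and month missing, and all 21,056 with no date.

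**The case against.** **The trigger is narrow.** Onset and resolution are both required fields and AEs are elicited at every visit. A false GTI1401 TEAE needs an onset within at most 21 days, an incomplete start date and a known end before infusion. This stands, and it limits the size of the problem.

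**The default is conservative and visible.** The listing shows start, end and TEAE flag for each event, and with about three subjects a wrong flag would be noticed. That helps a reader of the listing, but the summary tables would still be wrong. The conservative default is justified by lack of evidence, and here there is evidence.

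**The definition governs.** A programmer could treat the definition as overriding the conditions. But the SAP states without qualification that events meeting them will be considered treatment-emergent, so a literal program flags them.

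**Stronger readings.** A reader might infer that GTI1401 events will be counted in both studies, because the comparison is made with the first dose of each study. The documents do not establish this. The SAP never says that GTI1401 AE records feed the extension derivation, it presents the two studies separately (section 5), and the wording can equally mean that each study's AEs are compared with that study's own first dose. Double appearance of continuing events is intended. A reader might also infer that, since the conditions have no upper limit, extension events leak into GTI1401. The definition already closes the GTI1401 window at its final visit, and a leak would again need a pooled derivation that the SAP does not describe.

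**Conclusion.** The concern holds for GTI1401. The incomplete-date rule omits a field that the trial collects, and it therefore classifies as treatment-emergent some events that the SAP's own definition excludes. For the extension the same fault is possible, but only if GTI1401 records enter that derivation.

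The practical size is small in expectation and uncertain. It depends on the number of AEs with incomplete start dates, which may be zero. The shift of 25 to 33 points should not be read as automatic: it needs an affected event in a subject with no other TEAE. The conditional percentages rest on the uniform-date assumptions above and show only that, once a start date is incomplete, misclassification is the usual result for a screening event.

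**What to change.** Add to the incomplete-date rule in SAP 11.1: *unless the AE end date (complete or partial) shows that the event ended before the first infusion of that study, in which case it is not treatment-emergent for that study.*

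State also that the conditions resolve only the unknown start, and that the TEAE definition in the same section still applies, including the GTI1401 final visit as the upper limit. Keep the rule that AEs continuing into the extension count as extension TEAEs.

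Do not instead assign a partially dated AE only to the study in which it was first recorded. That would remove continuing events that the extension definition deliberately includes, and it is ambiguous at Week 9, which is both the GTI1401 completion visit and the first week of the extension.

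The cost is two sentences and a small programming change, with no new data. Events whose end date is missing, ongoing or uninformative keep the present default. In all the modelled cases the end-date override removes the misclassification.

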At the Week 9 visit, subjects will be asked whether they would like to participate in the extension trial (GTI1401-OLE). Subjects intending to participate in the extension trial will be able to continue the treatment with intravenous infusions of 60 mg/kg of Alpha-1 MP for at least another year (subjects will be further asked whether they would like to continue the treatment at yearly intervals) for the purpose of evaluation of the safety of long-term Alpha-1 MP treatment. Subjects not intending to enter the extension trial will visit the study center for follow-up/study completion at 30 days (4 weeks) after the last dose of Alpha-1 MP (Week 12).

The entire design of this clinical trial is shown in Figure 4-1, and its schedule is provided in Appendix 1.

^a Final Visit/Early Termination = Follow-up/Final Evaluation Visit. Subjects who discontinue early from the study will need to complete this study visit 30days (4 weeks) after the last study drug infusion.
^b At the Week 9 Visit, subjects will be given the option to participate in the GTI1401-OLE. If they are enrolled in Study GTI1401-OLE, the Week 9 visit will be their End of Study Visit of GTI1401 study.

Figure 4-1 Overall study schema

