For any subject, all AEs that occur at any time from the beginning of Alpha-1 MP administration until the final visit of the clinical trial will be considered as TEAEs.

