15. PLANNED TRIAL PERIOD

January 1, 2016 (IRB submission) to March 31, 2017 (Data lock)

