 11.1 Adverse Events
 11.1.7 Listing of AEs

Safety population

Subject Number	Start / End Date and Time of Events	Relative days *	MedDRA System Organ Class/ Preferred Term/ Verbatim Term	Pattern/ Seriousness / Severity / Action Taken with Study Drug	Causality to Study Drug / Outcome	(a)	(b)	Concomitant Medication/ Other Action
xxxx	yyyy-mm-ddThh:mm / yyyy-mm-ddThh:mm	x	xxxx/ yyyy/ zzzz	INTERMITTENT/ N / MILD / DRUG WITHDRAWN	DOUBTFUL/UN LIKELY/ RECOVERING/ RESOLVING	Y	N	N/ N
xxxx	yyyy-mm-ddThh:mm / yyyy-mm-ddThh:mm	x		CONTINUOUS/ N/ MILD / MODERATE	DEFINITE / RECOVERED / RESOLVED WITH	Y	Y	N/ N
xxxx	yyyy-mm-ddThh:mm / yyyy-mm-ddThh:mm	x	xxxx/yyyy/zzzz xxxx/ yyyy/ zzzz	CONTINUOUS N/ MILD / MODERATE	SEQUENT AE DEFINITE / RECOVERED / RESOLVED WITH	N	Y	Y (xxxxx)/ Y (xxxxx)
...

* Study start date =< Onset date of event: Onset date of event - Study start date + 1,

Study start date > Onset date of event: Onset date of event - Study start date

* (a)TEAE / (b)Did the subject withdraw from the study?

>Listing for "11.1.11 Listing of AEs leading to Premature Discontinuation from the Study" will be also provided in same layout.

>Row 4 column 3 will be changed to "11.1.11Listing of AEs leading to Premature Discontinuation from the Study"

>Sort order;

GTI 1401
 11 Safety Analysis

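### The rule for adverse events with only the onset day missing compares month and year separately, so post-dose events after a year-end can fail every TEAE condition

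*SAP*

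**What the plan says.** SAP 11.1 lists four alternative conditions under which an event with an incomplete start date is treatment-emergent. In the order listed:

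1. Day and month are missing, and the year is the first-dose year or later.
2. "Day is missing, month is present and the month is equal or after the month of first dose of each study (1401/1401-OLE", and in addition the year is the first-dose year or later.
3. "Day is missing and the year is equal to the year of the first infusion date of each study (1401/1401-OLE", and the month is the first-infusion month or later.
4. The whole date is missing.

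The definition in the same section contains no calendar-month test. For GTI1401 a TEAE is "any adverse event occurred after or on the first study drug infusion of GTI 1401 to the final visit of GTI 1401", with a parallel definition for the extension study. Protocol 5.3.3 agrees, covering "all AEs that occur at any time from the beginning of Alpha-1 MP administration until the final visit of the clinical trial". For subjects who enter the extension, "the Week 9 visit will be their End of Study Visit of GTI1401 study"; the others are followed to Week 12.

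SAP 11.1 then states: "All tables regarding to Adverse Events are restricted to TEAE". The layout for listing 11.1.7 carries a TEAE flag per event ("a)TEAE / (b)Did the subject withdraw from the study").

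**The concern.** A partial-date rule should settle cases in which the known part of the date leaves it unclear whether onset came before or after first dose. When the onset year is later than the first-dose year there is nothing to settle, because the event is post-dose whatever its month. Condition 2 nevertheless still requires the month number to be at least that of first dose.

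Safety is the primary objective of both studies (SAP 3.1). An event that meets no condition would be missing from the AE overview and from the system organ class, causality and severity tables. It would remain only in the listings, with a wrong TEAE flag. For these dates the error can only remove events, whereas conditions 1 and 4 and the worst-case handling of missing severity or relationship (SAP 5.2) lean towards inclusion.

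Treatment can cross a year-end in both studies. The planned period for GTI1401 is "January 1, 2016 (IRB submission) to March 31, 2017 (Data lock", and SAP 3.1 gives the extension about a year or more.

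**Working it through.** **Logic.** Let the first dose fall in year Y0 and month M0, and let onset be known as year Y and month M with the day missing.

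- Condition 1 does not apply, because the month is known.
- Condition 2: M ≥ M0 and Y ≥ Y0.
- Condition 3: Y = Y0 and M ≥ M0. Whenever this holds, condition 2 also holds, so it adds no case.
- Condition 4 does not apply, because the date is not wholly missing.

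The rule therefore reduces to condition 2. Take first dose November 2016 and onset January 2017: Y ≥ Y0 is true (2017 ≥ 2016), M ≥ M0 is false (1 ≥ 11), so the event is not a TEAE. Recorded as 2017 only, the same event meets condition 1; with no date at all it meets condition 4. Knowing more of the date removes the flag.

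Crossing 12 first-dose months with 12 onset months in the following year gives 144 pairs. Those with M < M0 fail: 12 × 11 / 2 = 66.

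**Reach.** The documents give neither first-dose dates nor a count of day-missing events, so the first-dose dates below are assumed. The measure is the share of on-study onset days, counting both end days, on which a day-missing event would meet no condition. Week 9 is day 56 (8 × 7), giving 57 days. Week 12 is day 77 (11 × 7), giving 78 days.

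| Assumed first dose | To Week 9 (extension entrants) | To Week 12 (others) |
|---|---|---|
| 1 Nov 2016 | 0/57 = 0% | 17/78 = 22% |
| 15 Nov 2016 | 10/57 = 18% | 31/78 = 40% |
| 1 Dec 2016 | 26/57 = 46% | 47/78 = 60% |
| 15 Dec 2016 | 40/57 = 70% | 61/78 = 78% |

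For example, 15 November plus 56 days is 10 January 2017, so 10 of the 57 days fall in January. The earliest affected first dose in 2016 is 6 November for Week 9 (56 of 366 possible dates affected) and 16 October for Week 12 (77 of 366).

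**Extension study, Ext Weeks 1 to 53 (days 0 to 364, 365 days).** The affected days are those in the following year that fall before the start month:

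- January start: 0%.
- June start: 151/365 = 41%.
- October start: 273/365 = 75%.
- December start: 334/365 = 92%.

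Over all 366 start dates in 2016 the mean is 61,087/133,590 = 45.7%. That average is meaningful only if starts are spread evenly over the year.

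**After the fix.** With the joint comparison, Y > Y0, or Y = Y0 and M ≥ M0, no enumerated post-dose onset is missed in any of the windows.

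**The case against.** Four points can be made for the plan as written.

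- **The list says if, not only if.** An event that meets none of the conditions is not declared non-treatment-emergent, and the general definition would still capture it. That is true as a matter of wording. But nothing tells the programmer to go back to the definition, and the natural coding sets the flag to No when no condition is met. The rule and the definition remain at odds.
- **Month could be read chronologically,** so that January 2017 is after November 2016. Condition 2's separate year test would then be redundant. The reply that the literal reading makes condition 3 redundant is fair, so redundancy alone does not decide the matter. The SAP does not state the chronological reading, however, and a rule open to both needs rewording in any case.
- **The trigger is rare and the event stays visible.** Onset date and time are required on the CRF (Protocol 5.3.7). AEs are assessed at every GTI1401 visit and at the weekly extension visits (SAP Appendices 1 and 2), and the target is at least 3 subjects. A misflagged event would still appear in the listings with its start date. This stands, and it limits the expected number of affected events, particularly in the extension, where the exposure percentages are largest.
- **The Week 12 window is not unique.** The protocol also places that visit 30 days after the last dose, which is day 49 + 30 = 79. The four Week 12 shares then become 19/80, 33/80, 49/80 and 63/80 (24%, 41%, 61% and 79%), and the earliest affected first dose becomes 14 October. The change is small.

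**Conclusion.** The concern holds. On its text, the partial-date rule fails to classify as treatment-emergent some events that SAP 11.1 and Protocol 5.3.3 define as TEAEs. It does so exactly when onset falls in a later year and in a lower-numbered month than first dose.

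In GTI1401 this requires a first dose from about mid-October (follow-up to Week 12) or 6 November (to Week 9). In the extension study any start outside January can be affected within Ext Weeks 1 to 53.

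The percentages are exposure under assumed first-dose dates, given an event with only its day missing. They are not expected losses; the number of events actually affected is likely to be small and may be zero. If one does occur, the number of subjects matters: with 3 subjects, a single subject wrongly dropped from a row changes that row by 1/3, or 33 percentage points. The conclusion rests on the listed conditions being programmed as the operative rule.

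**What to change.** Replace the second and third conditions in SAP 11.1 with one:

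*Day missing, month and year known: treatment-emergent if the onset year is later than the year of the first infusion of the study concerned, or if the years are equal and the onset month is the same as or later than the month of that infusion.*

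Conditions 1 and 4 can stay as they are. The cost is one sentence in the SAP and one line of derivation code; no additional data are needed.
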